3. INCLUSION AND EXCLUSION CRITERIA

Inclusion Criteria

Cancer Patient:

To be included in this study, participants must meet the following criteria:

1. Age 18 years old or older (no upper limit).
2. English speaking.
3. Diagnosed with stage Tis, Ta, or T1 bladder cancer.
4. Resides in the Western New York catchment area.
5. Did not receive a partial or radical cystectomy.
6. Does not have a prior cancer diagnosis within 12 months of their bladder cancer diagnosis.
7. Does not have a subsequent more advanced bladder cancer diagnosis.
8. For Roswell Park Cancer Registry only: Bladder cancer diagnosed 2016-2018, 2019-current.
9. Participant must understand the investigational nature of this study and sign an Independent Ethics Committee/Institutional Review Board approved written informed consent form prior to receiving any study related procedure.

Physician:

To be included in this study, physicians must meet the following criteria:

1. English speaking.
2. Physician in a clinic located in the catchment area.
3. Currently treats bladder cancer patients.

Refer to **Appendix A** for the Investigator Study Eligibility Verification Form: Inclusion Criteria.

Exclusion Criteria

Cancer Patient:

Participants Recruitment will be excluded from this study for the following:

1. Participants who have had chemotherapy or radiotherapy within 4 weeks (6 weeks for nitrosoureas or mitomycin C) prior to entering the study or those who have not recovered from adverse events due to agents administered more than 4 weeks earlier.
2. Participants with known brain metastases should be excluded from this clinical trial because of their poor prognosis and because they often develop progressive neurologic dysfunction that would confound the evaluation of neurologic and other adverse events.
3. Adults unable to consent.
4. Adults unable to complete study measures in English.
5. Individuals who are not yet adults (infants, children, teenagers).
6. Uncontrolled intercurrent illness including, but not limited to, ongoing or active infection, symptomatic congestive heart failure, unstable angina pectoris, cardiac arrhythmia, or psychiatric illness/social situations that would limit compliance with study requirements.
7. Unwilling or unable to follow protocol requirements.

Physician:

1. Unable to complete the study measures in English.

Refer to **Appendix B** for the Investigator Study Eligibility Verification Form: Exclusion Criteria.

Inclusion of Women and Minorities

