If individual will turn 18 BEFORE the current round of recruitment closes, age ineligibility applies and this script is read:

Applicant Turning 18 Soon

I'm sorry _____, you are not eligible to participate in the program. The program is made for those aged 18 and older.

Would you like to continue with the questionnaire? Yes No

If answer is YES, continue to Question 8.

If answer is NO, thank applicant for his/her interest in the program and End Interview.

IF THE INDIVIDUAL PASSES THESE SET OF QUESTIONS CONTINUE TO THE NEXT SECTION.

Cancer

8. Have you been diagnosed with stage Tis, Ta, or T1 bladder cancer? These are early stages of bladder cancer where the cancer lesion stays in the superficial layer of the bladder wall and does not invade the muscle layer. Sometimes they are called superficial bladder cancer or non-muscle invasive bladder cancer.

If YES, continue to Question 9.

If DON'T KNOW, continue to Question 9.

If NO, read this script:

I'm sorry, _____, you are not eligible to participate in the program. The program is designed for people who have been diagnosed with stage Tis, Ta, or T1 bladder cancer. Thank you for your interest, but we will not be able to enroll you.

9. Have you received a partial or radical cystectomy? A cystectomy is surgery where a part or the entire bladder is removed.

If NO, continue to Question 10.

If YES, read this script:

I'm sorry, _____, you are not eligible to participate in the program. The program is designed for people who have NOT received a partial or radical cystectomy. Thank you for your interest, but we will not be able to enroll you.

10. Have you had been diagnosed with another cancer (other than bladder cancer) during the past 12 months?

If NO, continue to Question 11.

If YES, read this script:

I'm sorry, _____, you are not eligible to participate in the program. The program is designed for people who have NOT been diagnosed with another cancer in the past 12 months of your being diagnosed with bladder cancer. Thank you for your interest, but we will not be able to enroll you.

11. Have you had chemotherapy or radiotherapy within the last 2 months?

If NO, continue to Question 12.

If YES, read this script:

I'm sorry, _____, you are not eligible to participate in the program. The program would not be safe for those who have had chemotherapy or radiotherapy within the last 2 months. Thank you for your interest, but we will not be able to enroll you.

Medications/Health

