- 7. Some other source

7. We would like to confirm your current address. Do you still live at _____? Read address from database.

1 Yes

0 No (please specify current address):

(Name of street, city, state, zip) update if necessary

BLADDER CANCER DIAGNOSIS

The next set of questions is about your bladder cancer diagnosis.

8. We would like to confirm the date of your bladder cancer diagnosis. According to our records, you were first diagnosed on _____. Is that correct?

1 Yes

0 No →

8 Don't Know

9 Refused

8a. What was the date? _____

8 Don't Know

9 Refused

9. Did your doctor use a scope to remove the bladder tumor? This procedure is called a transurethral resection.

1 Yes → 9a. What was the date? _____

0 No 8 Don't Know

8 Don't Know 9 Refused

9 Refused

10. Have you received any additional treatment for bladder cancer since your diagnosis?

1 Yes

0 No

8 Don't Know

9 Refused

If No, Don't Know or Refused, go to Question 14.

11. Did you receive chemotherapy (e.g., mitomycin C, thiotepa, doxorubicin)?

1 Yes

0 No

8 Don't Know

9 Refused

12. Did you receive immunotherapy (e.g., bacillus Calmette-Guerin [BCG], interferon)?

1 Yes

0 No

8 Don't Know

9 Refused

13. Did you receive any other treatment?

1 Yes → 13a. Specify: _____

0 No

8 Don't Know

9 Refused

CURRENT LIFESTYLE

The next section is about your current lifestyle. Again, this information is completely confidential.

14. What is your present height without shoes?

____ ft. ____ inches

8 Don't Know
9 Refused

15. How much do you currently weigh?

____ pounds

8 Don't Know
9 Refused

	Excellent	Very Good	Good	Fair	Poor	Don't Know	Refused
16. In general, would you say your health is:	5 	4 	3 	2 	1 	8 	9 
17. In general, would you say your quality of life is:	5 	4 	3 	2 	1 	8 	9 

18. What is the primary source of drinking water at your current residence?

1 Private Well
2 Community Supply (tap water, water filtered at home)
3 Bottled Water
4 Other (specify): _____
8 Don't Know
9 Refused

19. Over the past 30 days, how many glasses of water per day do you usually drink?

1 Less than 1 glass
2 1-2 glasses
3 3-4 glasses
4 5 or more glasses
8 Don't Know

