Appendix H New York State Cancer Registry Contact Materials and Procedures

POW-R Health: Power to Redefine your Health Program NYS Cancer Registry Patient Contact and Data Handling Procedures

The procedures described in this document are standard procedures the New York State Cancer Registry (NYSCR) follows for patient contact studies.

I. Approval Process

1. Roswell Park Cancer Institute IRB approval
2. NY State Health Department Administrative approval

II. NYSCR Patient Consenting Process (i.e., physician notification and patient consent to release name, contact information, and diagnostic information to Roswell Park Cancer Institute)

Using ICD-O-3 codes provided in the study protocol, the NYSCR will conduct a search of its database to identify eligible patients who were diagnosed with stage Tis, Ta, or T1 bladder cancer in 2018 or later, who resided in one of eight counties of interest at diagnosis (Niagara, Orleans, Genesee, Erie, Wyoming, Chautauqua, Cattaraugus, and Allegany), who are 18 years of age or older, who did not receive a cystectomy, who did not have a prior cancer diagnosis within 12 months of their bladder cancer diagnosis, who did not have a subsequent more advanced bladder cancer diagnosis, and who have not died or opted out of research studies. This search will be repeated if needed until the recruitment goal is reached. The NYSCR will contact reporting facilities to obtain the patients' physician information, if missing in the database.

The NYSCR will send a letter to the physician of record for selected cases notifying him/her that the patient was identified for the study, requesting that the NYSCR be notified if the patient is deceased, too ill or otherwise unable or ineligible to participate in the study, and requesting information about the case's primary care physician if different from the contacted physician. The physician will have three weeks to respond.

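### Phone-screen questions 10 and 11 can reject patients whom the eligibility criteria admit, and three study texts describe the planned 45-60 minute live call as 20 minutes

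*Combined protocol and SAP*

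**What the plan says.** **Other cancers.** Inclusion criterion 6 in section 3 is "Does not have a prior cancer diagnosis within 12 months of their bladder cancer diagnosis". The recruitment list in section 11 and the signed form in Appendix A repeat it, and the state registry search in Appendix H selects patients "who did not have a prior cancer diagnosis within 12 months of their bladder cancer diagnosis". Question 10 of the phone screen (Appendix E) instead asks "Have you had been diagnosed with another cancer (other than bladder cancer) during the past 12 months". A yes leads to a rejection text, which describes the program as meant for "people who have NOT been diagnosed with another cancer in the past 12 months of your being diagnosed with bladder cancer".

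**Recent treatment.** Exclusion 1 (section 3 and Appendix B) removes "Participants who have had chemotherapy or radiotherapy within 4 weeks (6 weeks for nitrosoureas or mitomycin C) prior to entering the study", and also "those who have not recovered from adverse events due to agents administered more than 4 weeks earlier". Question 11 asks "Have you had chemotherapy or radiotherapy within the last 2 months" and a yes again leads to rejection. The script asks neither which agent was given nor whether the patient has recovered.

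**Length of the live call.** Sections 10 and 11 plan one call of about 45-60 minutes. Both call scripts in Appendix Q tell the participant to expect about 60 minutes or 1 hour. The physician interview guide (Appendix I), the phone screen (Appendix E) and the registry's letter to physicians (Appendix H) all say 20 minutes.

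**Diagnosis years (minor and separate).** Criterion 8 admits Roswell Park registry patients diagnosed 2016-2018 and from 2019 on. Section 5 excludes those diagnosed in 2018-2019, so as not to overlap with the state registry list.

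**The concern.** The phone screen is the step that turns patients away. If its questions differ from the criteria, people whom the protocol admits are lost before anyone completes the eligibility forms. Section 5 already reports low enrollment from the state registry, so needless rejections are unwelcome.

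The call length matters mainly for the physician interviews. Section 11 makes the guide the physicians' overview of the program. Straight after hearing it, they say whether the program would suit their clinic and could be done there. The live call is the only live staff contact in the program, and the answers feed the exploratory endpoint in section 8. For patients, hearing 20 minutes at screening is a smaller matter of accurate description.

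**Working it through.** The plan gives no figure to reproduce here. The check sets the passages side by side and converts units.

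**1. Question 10.** Let D be the date of bladder cancer diagnosis and C the date of the call, in months.

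- Criterion 6, read as a cancer before the bladder diagnosis, covers D-12 to D. Question 10 covers C-12 to C. They overlap only if C-12 < D, that is C < D+12.
- If criterion 6 means 12 months on either side, it covers D-12 to D+12. The overlap then requires C-12 < D+12, that is C < D+24.
- For the 2018-2019 list, the latest D is 31 December 2019. No overlap remains for any call after 31 December 2020 (first reading) or 31 December 2021 (second reading).
- For the 2016-2018 part of criterion 8, the corresponding dates are 31 December 2019 and 31 December 2020.
- Section 11 mentions a revision of 21 March 2022. A call from then on to someone on the 2018-2019 list comes at least 26 months after diagnosis, beyond both limits.
- For more recent diagnoses (Appendix H searches 2018 or later; criterion 8 runs to the present) the windows can partly overlap. Example on the first reading: a call at D+6 asks about D-6 to D+6. It wrongly counts D to D+6 and misses D-12 to D-6.

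Where there is no overlap, a cancer reported in answer to question 10 cannot be one that criterion 6 excludes. The opposite error, passing someone whose other cancer preceded an older bladder diagnosis, is largely caught by the registry search and by Appendix A.

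**2. Question 11.** Take entry to the study as the day of the call. Two calendar months are 59-62 days, and 59/7 = 8.43 and 62/7 = 8.86 weeks.

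| Exclusion 1 window | Excess of the 2-month question |
|---|---|
| 4 weeks = 28 days | 31-34 days (4.4-4.9 weeks) |
| 6 weeks = 42 days | 17-20 days (2.4-2.9 weeks) |

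The 2-month window contains both protocol windows. For treatment given before the call, the question can therefore only over-exclude on timing. Some patients in the excess interval would be excluded anyway as not recovered, and Appendix B checks that clause.

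**3. Call length.** 45/20 = 2.25 and 60/20 = 3. The planned call is 2.25-3 times as long as the one described to physicians and patients, a difference of 25-40 minutes.

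**4. Number affected.** The documents do not say how many patients have another cancer in the relevant months, or recent chemotherapy or radiotherapy. The number wrongly rejected cannot be computed.

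**The case against.** **Question 10 is a slip of wording.** The rejection text restores the right anchor, and every other statement of the criterion agrees. The intent is indeed clear. But the caller is routed by the answer to the question as asked, and a rejected patient never reaches Appendix A, where the correct wording stands.

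**A stricter first screen may be deliberate.** A 2-month window covers both protocol windows, so there is no need to ask the agent to keep ineligible patients out, and recovery is checked later. That stands as far as wrongful inclusion goes. No passage says that a longer window is intended, however, and the two texts still give different rules.

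**The 45-60 minutes was provisional.** Sections 10 and 11 do say that the program may change during adaptation. The call scripts in Appendix Q are the working documents, though, and they say about an hour.

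**Other papers may give the right length.** Physicians also receive Appendix J, and patients a consent form and an information sheet. None of these is in our copy. The mismatch is certain; its effect on what physicians finally understand is not.

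**Stronger readings that the documents do not support.**

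- A reader might set the 80 consents against a pool of at least 100 and infer a small fixed margin that wrongful rejections use up. Appendix H says the search is repeated until the recruitment goal is met, section 5 expects at least 400 eligible cases, and a second registry has been added. The pool can be refilled.
- A reader might infer that the exploratory endpoint is invalid. It is qualitative, the questions are open with probes, and Appendix J may correct the length.
- A reader might multiply the extra minutes by the 40 intervention participants to get a staffing burden. That describes trial staff, not the physicians' clinics, whose patient volume is not given.
- A reader might infer bias between arms. Eligibility screening uses one script for everyone and does not depend on the assigned arm.

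**Conclusion.** The mismatches are real and stand in the current text. Followed as written, question 10 rejects some patients for a cancer outside criterion 6. This is certain to be wrong for calls more than 12 months after diagnosis (24 on the either-side reading) and partly wrong for earlier calls. Question 11 is longer than exclusion 1 by 31-34 or 17-20 days, taking entry as the day of the call, and errs only towards exclusion on timing. Physicians are told of a call one-third to under one-half as long as planned, unless Appendix J says otherwise.

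This should be corrected, because eligible patients can be turned away outright and the input to an exploratory endpoint is misdescribed. It affects who enters and what people are told. The comparison between arms, the sample size and the analysis do not change. The conflict over diagnosis years is minor: if criterion 8 is followed, section 5's aim of avoiding registry overlap is not met.

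**What to change.** - **Question 10:** reword it to criterion 6's anchor, using the diagnosis date from the registry that supplied the patient. The date is already to hand: the baseline questionnaire (Appendix F) reads it out with "According to our records, you were first diagnosed on". State whether criterion 6 means before the diagnosis only or either side.
- **Question 11:** reconcile it with exclusion 1. Which window applies is for the study team to decide.
- **Call length:** state one length in Appendices E, H and I, consistent with Appendix Q, before the physician interviews. Check the consent form, the participant information sheet and Appendix J against it.
- **Optional:** give questions 10 and 11 the referral to the principal investigator that question 12 already has.
- **Minor and separate:** reconcile the diagnosis years in criterion 8 (section 3, section 11 and Appendix A) with section 5.

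The cost is wording edits under an IRB amendment, plus review of the contact materials by the state registry and the state health department, as sections 24 and 27 require. Nothing changes in the sample size or the analysis.

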Appendix F Participant Baseline Bladder Questionnaire

Hi, my name is _____ . I'm calling because you kindly agreed to participate in the POW-R Health: Power to Redefine your Health Program. If you recall, part of being in the study is completing a survey—once before the study starts, and a final time after the study ends. The survey information will be used to see if our dietary intervention worked to improve your health. This phone survey will take about 45-60 minutes to complete. Do you have time to take the survey now?

If no: What would be a good day and time for me to call you? (please use Telephone Disposition Sheet)

If yes: Thank you! Please remember that everything you say here will be confidential. Your information won't be identified by name (proceed to questions below).

Let's start off with some information about you.

DEMOGRAPHICS

1. What is your marital status?

- 1 Married
- 2 Living as married
- 3 Divorced
- 4 Widowed
- 5 Separated
- 6 Single, never been married

2. What is the highest grade or level of schooling you completed?

- 1 Less than 8 years
- 2 8-11 years
- 3 12 years or completed high school
- 4 Post high school training other than college (vocational or technical)
- 5 Some college
- 6 College graduate
- 7 Postgraduate

3. Thinking about members of your family living in this household, what is your combined annual income, meaning the total pre-tax income from all sources earned in the past year?

- 1 \$0- \$9,000
- 2 \$10,000-\$14,999
- 3 \$15,000-\$19,999
- 4 \$20,000-\$34,999
- 5 \$35,000-\$49,999
- 6 \$50,000-\$74,999
- 7 \$75,000-\$99,999
- 8 \$100,000-199,999
- 9 \$200,000 or more

4. What is your occupational status?

- 1 Employed
- 2 Unemployed
- 3 Homemaker
- 4 Retired
- 5 Disabled
- 6 Other (Specify) _____

5. How many people currently live in your home (include yourself)? _____

6. Do you have any kind of health care coverage, including health insurance, prepaid plans such as HMOs or government plans such as Medicare, or Indian Health Service?

- 1 Yes (if yes, go to 6a)
- 2 No

6a. What is the primary source of your health care coverage?

- 1. A plan purchased through an employer or union (including plans purchased through another person's employer)
- 2. A plan that you or another family member buys on your own
- 3. Medicaid (primarily for people over age 65) or other state program
- 4. Medicare
- 5. TRICARE (formerly CHAMPUS), VA, or Military
- 6. Alaska Native, Indian Health Service, Tribal Health Service
- 7. Some other source

7. We would like to confirm your current address. Do you still live at _____? Read address from database.

1 Yes

0 No (please specify current address):

(Name of street, city, state, zip) update if necessary

BLADDER CANCER DIAGNOSIS

The next set of questions is about your bladder cancer diagnosis.

8. We would like to confirm the date of your bladder cancer diagnosis. According to our records, you were first diagnosed on _____. Is that correct?

1 Yes

0 No →

8 Don't Know

9 Refused

8a. What was the date? _____

8 Don't Know

9 Refused

9. Did your doctor use a scope to remove the bladder tumor? This procedure is called a transurethral resection.

1 Yes → 9a. What was the date? _____

0 No 8 Don't Know

8 Don't Know 9 Refused

9 Refused

10. Have you received any additional treatment for bladder cancer since your diagnosis?

1 Yes

0 No

8 Don't Know

9 Refused

If No, Don't Know or Refused, go to Question 14.

11. Did you receive chemotherapy (e.g., mitomycin C, thiotepa, doxorubicin)?

1 Yes

0 No

8 Don't Know

9 Refused

12. Did you receive immunotherapy (e.g., bacillus Calmette-Guerin [BCG], interferon)?

1 Yes

0 No

8 Don't Know

9 Refused

13. Did you receive any other treatment?

1 Yes → 13a. Specify: _____

0 No

8 Don't Know

9 Refused

CURRENT LIFESTYLE

The next section is about your current lifestyle. Again, this information is completely confidential.

14. What is your present height without shoes?

____ ft. ____ inches

8 Don't Know
9 Refused

15. How much do you currently weigh?

____ pounds

8 Don't Know
9 Refused

	Excellent	Very Good	Good	Fair	Poor	Don't Know	Refused
16. In general, would you say your health is:	5 	4 	3 	2 	1 	8 	9 
17. In general, would you say your quality of life is:	5 	4 	3 	2 	1 	8 	9 

18. What is the primary source of drinking water at your current residence?

1 Private Well
2 Community Supply (tap water, water filtered at home)
3 Bottled Water
4 Other (specify): _____
8 Don't Know
9 Refused

19. Over the past 30 days, how many glasses of water per day do you usually drink?

1 Less than 1 glass
2 1-2 glasses
3 3-4 glasses
4 5 or more glasses
8 Don't Know
9 Refused

20. Over the past 30 days, how often did you typically feel the need to empty your bladder during the day?

- 1 More frequently than once an hour
- 2 Once an hour
- 3 Once every 2 hours
- 4 Once every 3-5 hours
- 5 Only once or twice a day
- 8 Don't Know
- 9 Refused

21. Are you currently following any special diet?

- 1 Yes
- 0 No
- 8 Don't Know
- 9 Refused

If No, Don't Know or Refused, go to Question 23.

22. What type of special diet (check all that apply):

- 1 Vegetarian (with fish)
- 1 Vegetarian (no fish)
- 1 Vegan (no meat, chicken, fish, dairy, or eggs)
- 1 Macrobiotic
- 1 Paleo
- 1 Gluten-free
- 1 Atkins
- 1 Low Carb
- 1 Other (specify) _____
- 1 Don't Know
- 1 Refused

23 Do you currently smoke?

- 1 Yes, every day
- 2 Yes, some days →

23a. On how many of the past 30 days did you smoke a cigarette?

____|____| Days
8 Don't Know
9 Refused

24. On average, how many cigarettes do/did you smoke each day? (Note to interviewer: 1 pack=20 cigarettes)

____ Cigarettes per day

8 Don't Know
9 Refused

25. Over the last 30 days, how many days per week did you exercise for 20 minutes or more?

None
 1-2 days
 3-4 days
 5 or more days

26. Compared to other people your age, how would you rate the level of your usual physical activity? (If currently ill, think about your activity during the past 30 days before your illness).

Much more active
 More active
 About the same
 Less active
 Much less active

DIETARY INTAKE

These next questions are about the fruits and vegetables you ate or drank during the **past 30 days**. Please think about all forms of fruits and vegetables including cooked or raw, fresh, frozen or canned. Please think about all meals, snacks, and food consumed at home and away from home.

27. During the past month, how many times per week did you drink 100% PURE fruit juices? Do not include fruit-flavored drinks with added sugar or fruit juice you made at home and added sugar to. Only include 100% juice.

____ times per week

28. During the past month, not counting juice, how many times per week did you eat fruit? Count fresh, frozen, or canned fruit.

____ times per week

29. During the past month, how many times per week did you eat cooked or canned beans, such as refried, baked, black, garbanzo beans, beans in soup, soybeans, edamame, tofu or lentils. Do NOT include long green beans.

____ times per week

30. **During the past month, how many times per week did you eat dark green vegetables for example broccoli or dark leafy greens including romaine, chard, collard greens or spinach?**

 times per week

31. **During the past month, how many times per week did you eat orange-colored vegetables such as sweet potatoes, pumpkin, winter squash, or carrots? (write number)**

32. **Not counting the vegetables mentioned, about how many times per week did you eat OTHER vegetables? Examples of other vegetables include tomatoes, tomato juice or V-8 juice, corn, eggplant, peas, lettuce, cabbage, and white potatoes that are not fried such as baked or mashed potatoes. (write number)**

 times per week

These next questions are about other vegetables you ate during the **past 30 days**. Please think about all meals, snacks, and food consumed at home and away from home.

(Go through table. Frame questions as, “How often did you eat raw arugula? Never, a few times per year, once per month, 2-3 times per month, once a week, twice per week, 3-4 times per week, 5-6 times per week, or every day.” If they answer never, go to the next vegetable. If they ate any amount, ask, “About how much raw arugula did you eat each time? The medium serving size is one cup of the vegetable, about the size of a baseball. Lightly cooked generally includes stir fry, sauté, microwave, short-term, e.g. less than 10 minutes, steam or bake, and thoroughly cooked includes stew, biol, or long-term, e.g. more than 10 minutes, steam or bake.)

Vegetables

		Never	A Few Times Per Year	Once per month	2-3 Times per month	Once per week	Twice per week	3-4 Times per week	5-6 Times per week	Every day	How much each time?		
											S	M	L
Arugula	raw												
	lightly cooked (e.g. stir fry)												
	thoroughly cooked (e.g. stew)												
Broccoli	raw												
	lightly cooked (e.g. stir fry)												
	thoroughly cooked (e.g. stew)												
Broccoli sprout	raw												
	lightly cooked (e.g. stir fry)												
	thoroughly cooked (e.g. stew)												
Broccolini	raw												
	lightly cooked (e.g. stir fry)												
	thoroughly cooked (e.g. stew)												
Corn	raw												
	lightly cooked (e.g. stir fry)												
	thoroughly cooked (e.g. stew)												

Green cabbage	raw (e.g. coleslaw)											
	lightly cooked (e.g. stir fry)											
	thoroughly cooked (e.g. stew)											
Red/Purple cabbage	raw											
	lightly cooked (e.g. stir fry)											
	thoroughly cooked (e.g. stew)											
Sauerkraut	raw											
	lightly cooked (e.g. stir fry)											
	thoroughly cooked (e.g. stew)											
Carrots	raw											
	lightly cooked (e.g. stir fry)											
	thoroughly cooked (e.g. stew)											
Cauliflower	raw											
	lightly cooked (e.g. stir fry)											
	thoroughly cooked (e.g. stew)											
Brussels sprouts	raw											

	lightly cooked (e.g. stir fry)										
	thoroughly cooked (e.g. stew)										
Kale	raw										
	lightly cooked (e.g. stir fry)										
	thoroughly cooked (e.g. stew)										
Kohlrabi	raw										
	lightly cooked (e.g. stir fry)										
	thoroughly cooked (e.g. stew)										
Collard greens	lightly cooked (e.g. stir fry)										
	thoroughly cooked (e.g. stew)										
Peas	raw										
	lightly cooked (e.g. stir fry)										
	thoroughly cooked (e.g. stew)										
Mustard greens	raw										
	lightly cooked (e.g. stir fry)										
	thoroughly cooked (e.g. stew)										
Turnip	lightly cooked (e.g. stir fry)										
	thoroughly cooked (e.g. stew)										

Turnip greens	lightly cooked (e.g. stir fry)										
	thoroughly cooked (e.g. stew)										
Bok/ Pak choy	raw										
	lightly cooked (e.g. stir fry)										
	thoroughly cooked (e.g. stew)										
Chinese cabbage/ Napa	raw										
	lightly cooked (e.g. stir fry)										
	thoroughly cooked (e.g. stew)										
Daikon root	raw										
	lightly cooked (e.g. stir fry)										
	thoroughly cooked (e.g. stew)										
Celery	raw										
	lightly cooked (e.g. stir fry)										
	thoroughly cooked (e.g. stew)										
Garden cress	raw										
	lightly cooked (e.g. stir fry)										
	thoroughly cooked (e.g. stew)										
Water cress	raw										

	lightly cooked (e.g. stir fry)										
	thoroughly cooked (e.g. stew)										
Radicchio	lightly cooked (e.g. stir fry)										
	thoroughly cooked (e.g. stew)										
Radishes	raw										
	lightly cooked (e.g. stir fry)										
	thoroughly cooked (e.g. stew)										

We're going to finish the survey by asking some final questions about sauces and condiments you ate during the **past 30 days**. Please think about all meals, snacks, and food consumed at home and away from home.

(Go through table. Frame questions as, "How often did you eat mayonnaise? Never, a few times per year, once per month, 2-3 times per month, once a week, twice per week, 3-4 times per week, 5-6 times per week, or every day." If they answer never, go to the next food. If they ate any amount, ask, "About how much mayonnaise did you eat each time? The size of your thumb from knuckle to tip or less? About two thumbs worth? Or more than 2 thumbs worth?"

For **horseradish**, if they consume any amount, ask, "about how much horseradish did you eat each time? Smaller than an egg, about the size of egg, or more than the size of an egg?")

SAUCES AND CONDIMENTS											
	Never	A Few Times Per Year	Once per month	2-3 Times per month	Once per week	Twice per week	3-4 Times per week	5-6 Times per week	Everyday	Medium Serving	Serving Size
											S
											M L
Mayonnaise and mayonnaise-type spreads		2 Tbsp.	  								
Horseradish		1/4 cup	  								
Mustard		2 Tbsp.	  								
Wasabi		2 Tbsp.	  								

[figure not shown]
Belief into Action Scale

Circle a single number for each question below:

[figure not shown]
1. Please circle the highest priority in your life now? (most valued, prized)

1. My health and independence
2. My family
3. My friendships
4. Job, career or business
5. My education
6. Financial security
7. Relationship with God
8. Ability to travel & see the world
9. Listening to music and partying
10. Freedom to live as I choose

[figure not shown]
2. How often do you attend religious services? (circle a number below)

[figure not shown]
3. Other than religious services, how often do you get together with others for religious reasons (prayer, religious discussions, volunteer work, etc.)?

[figure not shown]
4. To what extent (on a 1 to 10 scale) have you decided to place your life under God's direction?

[figure not shown]
5. What percentage of your gross annual income do you give to your religious institution or to other religious causes each year?

[figure not shown]
6. On average, how much time each day (in 24 hrs) do you spend listening to religious music or radio, or watching religious TV?

[figure not shown]
7. On average, how much time each day do you spend reading religious scriptures, books, or other religious literature?

[figure not shown]
8. On average, how much time each day do you spend in private prayer or meditation?

9. On average, how much time each day do you spend as a volunteer in your religious community or to help others for religious reasons?

10. To what extent (on a 1 to 10 scale) have you decided to conform your life to the teachings of your religious faith?

You have finished the survey! Thank you so much for your time. Do you have any questions?

Again, welcome to POW-R Health Program!

